6.8 Concomitant Therapy

Record in the CRF all concomitant therapies (e.g., medicines or nondrug interventions, including topical creams and ointments) used from the time the participant signs the informed consent until completion of the study, including any changes. For prescription and over-the-counter medicines, COVID-19, and other vaccines, vitamins, and herbal supplements, record the name, reason for use, dates administered, and dosing information.

[figure not shown]
Contact the Medical Monitor for any questions on concomitant or prior therapy.

6.8.1 Corticosteroids

Long-term use of CS should be minimized since its use has been associated with damage, morbidity and mortality in SLE (Doria 2014, Gladman 2003, Ruiz-Irastorza 2012, Thamer 2009, Urowitz 2012). Inhibitors of type I IFN pathway are potentially corticosteroid-sparing by increasing glucocorticoid sensitization (Guiducci 2010, Buckland 2010, Northcott 2021). In order to demonstrate the potential CS-sparing effect of enpatoran and its treatment effect compared with placebo, it is critical that medical management of these participants must include continuous attempts to taper CS use.

Beginning at Week 2 (\sim Day 15) and continuing through Week 12, CS MUST be tapered to a prednisone-equivalent dose of \leq 5 mg/day as clinically tolerated (see protocol-specified CS tapering guidance in Appendix 7).

[figure not shown]
IMPORTANT: The Investigator must be familiar with and follow the rules for CS dosage during the study (see details of the CS rules and protocol-specified tapering guidance, in Appendix 7). Investigators may adjust the CS dosage of participants, if deemed clinically necessary, in a manner not according to the protocol-specified rules; CCI

6.8.2 Corticosteroids Rescue Medication

The following CS rescue rules will apply during the 24-Week DBPC period for participants in Cohort A or Cohort B:

Control of disease activity/flare with a brief steroid rescue is allowed only once after Day 1 through Week 8. During this period, participants may increase the CS dose up to 30 mg/day prednisone-equivalent or use 1 intramuscular CS injection as rescue for worsening of SLE or CLE activity but must be tapered within 7 days to \leq CS dose used before the rescue (if not on any CS before the rescue, tapering within 7 days to \leq mg/day is allowed).

6.8.3 Permitted Medicines

All background therapy for SLE and CLE given prior to Screening must be stable or discontinued according to the specifications in the exclusion criteria for a participant to be eligible for the study (see Section 5.2 for Screening Period and Appendix 6 for additional details on SLE/CLE background therapy). As changes in standard SLE or CLE therapy can affect disease activity and PD endpoints, confounding the study findings, all background antimalarial, and immunosuppressant therapies should remain stable during the Screening and 24-Week DBPC Periods. In addition, medication should NOT be adjusted or discontinued prior to Screening in order to allow the participant to become eligible.

The only permitted medications are the following:

- 1. Any medications required per the medical history and not specifically prohibited by the protocol during the study (i.e., from Screening Visit to the End of the study).
- 2. COVID-19 vaccines. See Section 2.3.3.
- 3. Vaccination with a subunit or inactivated vaccine (e.g., influenza virus, S. pneumoniae) is allowed providing that vaccination completes 2 weeks before any study visit.
- 4. CS dose up to daily equivalent of prednisone 30 mg maximum for SLE and CLE participants (see Appendix 7). Inhaled CS (asthma, COPD) with requirement for stable dose during the study. Use of 1 intramuscular injection after Day 1 through Week 8 as a rescue.
- 5. Topical CSs: Class II-VII in stable application for ≤ 4 weeks, up to 2 times per day, except augmented betamethasone dipropionate 0.05% gel or ointment (Table 11).

[figure not shown]
- 6. Topical calcineurin inhibitors in stable application up to 1 time per day. Oral tacrolimus up to 0.1 mg/kg.
- 7. Use of 1 antimalarial such as hydroxychloroquine (up to 400 mg/day) or chloroquine (up to 500 mg/day) is permitted; doses should remain stable. For any changes in doses, the Medical Monitor should be contacted, and then the changes should be carefully noted.
- 8. Permitted SoC therapy during the study for SLE and CLE including the use of 1 of the following single immunosuppressants or immunomodulators (see Appendix 6 for maximum permitted doses in each case):
 - AZA
 - 6-mercaptopurine
 - Mycophenolate (either as MMF or mycophenolate sodium)
 - MTX
 - Sulfasalazine
 - Leflunomide
 - Dapsone
 - Retinoids

Note: these medications must be stable throughout the 24-Week DBPC period periods in addition to the Screening Period, see Section 5.2.

Although it is expected participants will be on SoC medications, not all therapies are permitted, as detailed in Section 6.8.4.

- 1. NSAID may be used as needed for temporary relief of symptoms. Any changes in NSAIDs up to 1 day prior to each study visit that could affect assessments (e.g., pain) should be avoided.
- 2. Vitamin D and calcium supplementation are encouraged per local SoC guidelines. Participants not already taking these medications at Screening should, according to the Investigator's judgment, initiate treatment as soon as possible after Screening. These medications will not be supplied by the Sponsor.
- 3. Low-dose aspirin (\leq 350 mg/day) for cardiovascular prophylaxis or other indications.
- 4. Stable dose and regimen of anticoagulants.
- 5. Treatment with a stable dose of over-the-counter supplements (nonherbal [e.g., iron supplement] is allowed if initiated before the Screening Visit). See Section 6.8.3 and Appendix 6 for prohibited supplements.
- 6. Paracetamol (acetaminophen) up to 3 g/day may be initiated or continued for pain control of SLE symptoms during the study. This should be titrated off as tolerated.
- 7. Opioids are permitted for stable use for SLE if initiated by Day 1. Initiation of opioids and/or as needed dosing of opioids for more than 2 weeks after Day 1 for SLE is not permitted. These may be titrated off as tolerated during the study.

- 8. Analgesics may be used at stable doses or as needed basis for temporary relief of symptoms not due to SLE. Any changes in analgesics up to 1 day prior to each study visit that could affect the assessments (e.g., pain) should be avoided (see Section 6.8.4 and Appendix 6 for prohibited medicines).
- 9. It is recommended that angiotensin-converting enzyme inhibitors and angiotensin receptor blockers if used at Screening be maintained at a stable dose during the study for safety reasons (e.g. hypertension, cardiac failure etc.). Participants with certain degrees of lupus nephritis (≤ 339 mg/mmol by spot UPCR) will be permitted into the study and the proteinuria will be followed, unless dose change, or initiation is required for safety reasons.
- 10. Medications for the treatment of infections and hypersensitivity reactions will be provided at the discretion of the Investigator. If systemic CS are deemed necessary, their use should follow the guidelines in Appendix 7, unless deviation from these guidelines are deemed medically necessary.
- 11. Any medicines that are considered necessary to protect the participant's welfare in emergencies may be given at the Investigator's discretion, regardless of if it results in a protocol deviation and the Medical Monitor must be informed.

16. Sunscreen.

6.8.4 Prohibited Medicines

The following types of medication are not permitted during the study; see Appendix 6 for further details on medication guidance and specific prohibited medications:

- 1. Immunomodulator or immunosuppressant therapies not listed in Section 6.8.3.
- 2. Use of more than 1 medication considered to have immunosuppressant or immunomodulatory properties, not including antimalarials, or CS.
- 3. Use of more than 1 antimalarial therapy.

- 4. Biologic therapies for SLE or CLE. Biologic therapies for other indications must be discussed with the Medical Monitor with the exception of insulin or denosumab, which are permitted.
- 5. Vaccines.
 - a. COVID-19 vaccines unauthorized and not approved by the country-specific health agencies. See Section 2.3.3.
 - b. Live or live attenuated virus vaccine.
 - c. Vaccination with a subunit or inactivated vaccine (e.g., influenza virus, S. pneumoniae) if vaccination completes < 2 weeks before study visit.
- 6. Supplements (herbal/nonherbal/Chinese Medication). Treatment with a stable dose of over-the-counter supplements (nonherbal) is allowed if nonherbal supplements are initiated before the Screening Visit (except for those stated in Appendix 6).
- 7. CSs > 30 mg daily prednisone-equivalent for SLE and CLE. See Appendix 7 for additional CS rules.
- 8. Topical CSs Class II–VII applied for > 4 weeks, or > 2 times per day. Topical CSs Class I and augmented betamethasone dipropionate 0.05% gel or ointment are not allowed (Table 11).
- 9. Topical calcineurin inhibitors applicated > 1 time per day. Initiation of, or change in, dosing of an angiotensin-converting enzyme inhibitor or angiotensin receptor blocker.
- 10. Initiation or change in dose of anticoagulation or antiplatelet therapy.
- 11. Nonsteroidal anti-inflammatory drugs used above maximum prescribed dose per local label.

- 13. Other investigational agents not specified in this study.
- 14. Change in dosing or discontinuation of leflunomide less than 8 weeks prior to Screening.

Any medication administered during the study and related to an increase in CLE disease activity should be discontinued (e.g., proton pump inhibitors, terbinafine).

Any additional concomitant therapy that becomes necessary during the study and any change to concomitant therapies must be recorded in the corresponding section of the CRF, noting the name, dose, duration, and indication of each drug.

The SoC medications are part of the participant's SLE and CLE treatment prescribed by the treating clinician and will not be provided by the Sponsor.

CC

Refer to the exclusion criteria (Section 5.2) for prohibited medication uses before study enrollment.

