- 16. Any major surgery such as abdominal, thoracic, or joint replacement surgeries \leq 6 weeks prior to Screening Visit or planned major surgery during the study (including Follow-up).
- 17. History of alcohol or drug abuse ≤ 1 year prior to Screening Visit as per Investigator opinion.
- 18. History of splenectomy or functional asplenia.

CC

20. Any condition that could interfere with study objectives, conduct, or evaluation in the opinion of the Investigator or Sponsor/designee.

Prior/Concomitant Therapy (See Appendix 6 for further details)

- 21. Known hypersensitivity to any study intervention, component, or placebo.
- 22. Initiation or dose change of anticoagulation or antiplatelet therapy ≤ 4 weeks prior to Screening Period.

$\overline{\mathsf{CC}}$

- An unstable dose ≤ 3 months prior to Day 1, except for medications administered short term to treat acute symptoms (e.g., emesis), which is allowed.
- 24. The use, initiation, or dose change in the following therapies ≤ 2 weeks prior to Screening:
 - a. Use of CS exceeding 30 mg daily prednisone-equivalent for SLE and CLE (SCLE and/or DLE), including but not limited to oral, topical CSs Class I, and augmented betamethasone dipropionate 0.05% gel or ointment, intramuscular, or injectable CS (Table 11).
 - b. Use of topical calcineurin inhibitors more than 1 time per day.
 - c. Initiation or dose change of angiotensin-converting enzyme inhibitors or angiotensin receptor blocker, or NSAIDs, or use of NSAIDs above maximum prescribed dose per local label.
- 25. The initiation, use, or change in the following therapies \leq 4 weeks prior to Screening:
 - a. Vaccination with live or live attenuated virus vaccine.
 - b. Use of thalidomide or lenalidomide.
 - c. Use of intralesional therapies.
 - d. Use of tripterygium and total glucosides of paeony.
- 26. The initiation, use of a dose exceeding the maximum specified dose (see Appendix 6) or change in therapies < 8 weeks prior to Screening for any medication considered to have immunomodulating and/or immunosuppressant properties (e.g., antimalarials, MTX, 6-mercaptopurine, sulfasalazine, MMF, or sodium, AZA, dapsone, or retinoids). A stable dose of leflunomide is not exclusionary; however, participants having changed their dose or discontinued leflunomide must have done so at least 8 weeks prior to Screening.
- 27. The initiation, use or change in the following therapies \leq 12 weeks prior to Screening:

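### Protocol 6.8.4 bars every start or dose change of an ACE inhibitor or ARB, while 6.8.3 only recommends a stable dose and excepts changes needed for safety

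*Protocol*

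**What the plan says.** Protocol 6.8.4 opens with "The following types of medication are not permitted during the study". Item 9 of that list begins with topical calcineurin inhibitors and then, as a second sentence, adds "Initiation of, or change in, dosing of an angiotensin-converting enzyme inhibitor or angiotensin receptor blocker". The sentence carries no qualification and no pointer to another section.

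Protocol 6.8.3, second numbered list, item 9, treats the same drugs differently. It recommends that those already taken at Screening "be maintained at a stable dose during the study for safety reasons", with hypertension and cardiac failure as examples. Its next sentence admits participants with lupus nephritis up to a stated proteinuria limit and says the proteinuria will be followed. That sentence ends "unless dose change, or initiation is required for safety reasons".

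Before entry, exclusion criterion 24c in Protocol 5.2 covers "Initiation or dose change of angiotensin-converting enzyme inhibitors or angiotensin receptor blocker, or NSAIDs" in the 2 weeks before Screening, and Table 7 in Appendix 6 requires 2 weeks of stable dosing before Screening. Neither governs conduct after randomization.

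**The concern.** ACE inhibitors and ARBs are common in lupus patients with hypertension or renal involvement, and the protocol anticipates both. Blood pressure, renal function or tolerability can call for a new start or a dose change that is necessary but not an emergency. An investigator who consults 6.8.4 finds the change barred. One who consults 6.8.3 finds a recommendation with a safety exception.

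Two things follow. The main one is classification: one site may report the change as use of a prohibited medicine, another as ordinary permitted care. SAP 10.2.1 says that all deviations are documented in the study datasets and that important ones are tabulated by cohort and study intervention group, so the inconsistency could reach the reported deviation data. The lesser one is a small risk that a site reading 6.8.4 literally waits before making a change the participant needs.

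**Working it through.** The plan states no figure on this point and no arithmetic applies. The check is to apply each rule to the situations that can arise.

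| Situation during the study | 6.8.4 item 9 | 6.8.3 item 9 |
|---|---|---|
| Dose change, drug in use at Screening, no safety need | Barred | Advised against (recommendation only) |
| Dose change, drug in use at Screening, needed for safety, not an emergency | Barred | Excepted |
| New start, needed for safety, not an emergency | Barred | Excepted, through the closing clause only |

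The second and third rows are the direct conflict. The first is a difference in force between a recommendation and a prohibition.

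**Does the closing clause of 6.8.3 item 9 belong to these drugs?** Where it is printed, it would say that proteinuria is followed unless a dose is changed or a drug is started, which makes no sense. It fits only the dosing of ACE inhibitors and ARBs, the subject of the item. Without it, rows 1 and 2 would still set a recommendation against a prohibition, but row 3 would have no support in 6.8.3.

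**Does other visible text settle the matter?**

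- 6.8.3, first list, item 1 permits medicines the protocol does not specifically prohibit, and the sentence introducing the second list refers to 6.8.4 for what is not allowed. If these set an order of precedence, the prohibition wins and the safety exception is lost.
- 6.8.3, second list, item 11 says that medicines needed for a participant's "welfare in emergencies may be given at the" investigator's discretion, even if a deviation results. It covers emergencies only.
- 8.3.2 makes the investigator responsible for necessary further treatment, and 8.3.8 promises standard medical care for all adverse events. These support giving the care. They do not say that a listed prohibited change ceases to be prohibited.
- The closing part of 6.8.4 requires newly necessary therapy and changes to be recorded. That is a recording duty, not a permission.
- Section 6.8 directs questions to the Medical Monitor, who can explain the text. Section 8 allows no waivers or exemptions, so the Medical Monitor cannot set item 9 aside.

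**Do comparable pairs agree?** Anticoagulants do: 6.8.3 asks for a stable dose and regimen, and 6.8.4 item 10 bars a start or change. Topical calcineurin inhibitors do: both sections set the limit at once a day. The ACE-inhibitor/ARB pair does not.

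**The case against.** The best defence is that 6.8.3 item 9 is the specific safety exception to the general rule in 6.8.4 item 9. The protocol has a similar layout for corticosteroids: 6.8.3 item 10 lets systemic use for infection or hypersensitivity depart from Appendix 7 when medically necessary, while 6.8.4 item 7 states the dose ceiling without that exception. This is a fair reading and probably what the sponsor intended. It stands as evidence of intent, but neither ACE-inhibitor/ARB item refers to the other, so the reader has to supply the link.

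A reader might infer the opposite: because some 6.8.4 items carry their own qualification, such as "Immunomodulator or immunosuppressant therapies not listed in Section 6.8.3" or "with the exception of insulin or denosumab, which are permitted", item 9 must be deliberately absolute. The documents do not support that. Most visible items in the list have no qualification, some of those that do are only defining scope, and the corticosteroid example shows an exception held in 6.8.3 alone.

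It is also fair to say that care is unlikely to be withheld, given 8.3.2, 8.3.8 and the query route. That stands, and it is why deviation classification comes first here and delayed care second.

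**Conclusion.** The two items conflict for a start or dose change that is needed for safety but is not an emergency. The extent is one item in 6.8.4 against one item in 6.8.3. The documents give no rate for such changes, so no participant count is offered. This is a minor point worth correcting because the correction is cheap.

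A reader might infer that an ACE-inhibitor or ARB change would make a Cohort B participant a BICLA non-responder through the prohibited-medication rule. The documents do not support this. The treatment-failure definition in Protocol Appendix 8 leaves the decision to the Endpoint Adjudication Committee and spells out prohibited medication as immunosuppressives, antimalarials and non-compliant corticosteroid use. It does not name these drugs.

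The conclusion rests on two assumptions. First, the closing clause of 6.8.3 item 9 refers to ACE-inhibitor and ARB dosing; if it did not, only the conflict over dose changes in drugs already used at Screening would remain. Second, the visible text is what sites work from. The visible numbering jumps from 11 to 16 in 6.8.3 and from 11 to 13 in 6.8.4. Nothing is inferred from those gaps, and removed text that reconciled the items would dispose of the point.

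**What to change.** Make three edits to the protocol:

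1. In 6.8.4, move the ACE-inhibitor/ARB sentence out of the topical calcineurin inhibitor item into its own item, and end it with: *unless required for safety reasons (see Section 6.8.3)*. This adds eight words.
2. In 6.8.3 item 9, replace the recommendation with wording to this effect: *For participants taking an ACE inhibitor or ARB at Screening, a stable dose throughout the study is recommended. A dose change, or a start in participants not taking one at Screening, is permitted only if required for safety reasons (for example hypertension or cardiac failure).* Separating changes from starts matters, because a drug already in use at Screening cannot be started.
3. End the lupus nephritis sentence in the same item once it has said that the proteinuria will be followed, deleting the displaced clause.

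The edits can go into the next amendment, with a clarification letter to sites if one is wanted sooner. The SAP, the sample size and the adjudication process do not change.

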6.8.5 Other Interventions

Use of potentially excluded procedures such as acupuncture or joint replacement therapy is to be discussed with the Sponsor or designee on a case-by-case basis. Use of acupuncture is allowed to continue if it is started before the Screening Visit. Major elective surgeries such as abdominal, thoracic, or joint replacement surgeries should not be planned to occur in the Study Period. Unplanned joint replacement surgery should be discussed at the earliest opportunity prior to the surgery with the Medical Monitor regarding continuation of the participant in the study.

7 Discontinuation of Study Intervention and Participant Discontinuation/Withdrawal

7.1 Discontinuation of Study Intervention

7.1.1 Temporary Discontinuation

Study intervention may be stopped at any time at the Investigator's discretion; however, the Medical Monitor must be notified if the participant has missed doses of study intervention for at least 5 consecutive days. The participant will continue their scheduled visits. If the participant's temporary discontinuation is due to an AE, see Section 8. Consultation with the Medical Monitor prior to restarting study medication is advised.

If the participant is unable to resume study intervention, see Section 7.1.2.

7.1.2 Permanent Discontinuation

In rare instances, it may be necessary for a participant to permanently discontinue (definitive discontinuation) study intervention. If study intervention is definitively discontinued, the participant is encouraged to remain in the study until last safety follow-up (i.e., Week 26). The participant should complete the ET assessments as soon as possible and revert to the same study schedule (Table 1) based on the participant's Day 1 until the Safety follow-up visits are completed (see Section 1.3).

The participant must be withdrawn from study intervention in the event of any of the following:

- Enrollment despite violation of an exclusion criterion which, in the Investigator's, and/or Sponsor's opinion, makes discontinuation of the participant necessary.
- Participation in any other interventional study during the duration of this study for which the Investigator considers discontinuation of the study intervention necessary.
- Occurrence of pregnancy.
- Occurrence of a clinical condition (e.g., SAE, SFI defined severe flare) for which discontinuation is considered necessary by the Investigator and/or the Sponsor/designee.

- Non-compliance to study visits, study intervention etc., judged as significant by the Investigator or Sponsor, e.g., taking CCI of the study intervention doses.
- An unplanned event that necessitates discontinuation of study intervention for more than 4 weeks.
- If a participant is unblinded.

7.2 Participant Discontinuation/Withdrawal from the Study

- A participant may discontinue from the study at any time, at his/her own request or at the discretion of the Investigator for safety, behavioral, compliance, or administrative reasons.
- A participant is considered discontinued from the study due to death.
- A participant must be discontinued from the study in the event the participant is lost to follow-up.
- At the time of discontinuing from the study, if possible, a discontinuation visit (i.e., early termination visit) will be conducted, as listed in the SoA. The SoA specifies the data to collect at early termination and safety follow-up visits, and any additional evaluations that need to be completed.
- If the participant revokes consent for the study, any data collected up to that point may still be used, but no future data can be generated, and any biological samples collected will be destroyed.
- A participant has the right at any time to request destruction of any biological samples taken. The Investigator will document this in the site study records and the CRF and inform the Sponsor. The samples will be destroyed.

When a participant must be withdrawn from the study, the Investigator, or designee will inform the Medical Monitor immediately, who will then inform the Sponsor's medically responsible individual (or Medical Responsible).

